10.7.3. Part 1 Analyses

Part 1 will be analyzed separately as an a priori powered study. A Statistical Analysis Plan will be developed that describes the analyses to address the study's primary, secondary, and exploratory objectives.

The following provides an outline of the methods for the main comparisons between randomized arms, particularly for the primary outcome measure.

Analyses involving randomized comparisons will include all randomized participants who received the first (confirmed) dose of study treatment, according to a modified intention-to-treat (m-ITT) approach. Participants who do not receive the first (confirmed) dose will be replaced. Unless stated otherwise, the date of randomization will be the time origin for analysis (Day 1). Additional per-protocol analyses may be performed, particularly for virology efficacy endpoints. Missing data are expected to be uncommon (<5 to 10% of participants). Losses to follow-up will be assumed non-informative and complete-case analyses will be conducted.

This is a virology proof-of-principle study, as such a type I error probability of 10% (α =0.10) will be used throughout, with no planned adjustments for multiplicity or primary or secondary endpoints. Throughout, all statistical tests will be two-sided and "exact" statistical procedures that do not rely on large sample assumptions will be applied where computationally feasible.

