10.7.3.1. Primary Outcome Measures

Virologic Efficacy: The distribution of days until first non-detectable SARS-CoV-2 viral RNA in NP swabs will be estimated for each randomized arm (drug versus placebo), using Kaplan-Meier methods with a corresponding exact stratified log-rank test (Part 1 only: to account for the "early" versus "late" time from symptom onset randomization strata). "Non detectable" will be defined as a viral load below the limit of quantification (BLOQ). Two consecutive non-detectable viral RNAs in NP swabs (or one negative with no further follow-up) will be required to achieve the event. The date of the first non-detectable will be the event date. Participants who prematurely discontinue the study before achieving non-detectable results will have follow-up for efficacy endpoints censored at the date of last measurement. Losses to follow-up will be assumed non-informative.

Safety and Tolerability: In order to measure the safety and tolerability of EIDD-2801, we will estimate by randomization arm the probability of 1) any AEs leading to early discontinuation of blinded treatment (active or placebo), 2) study drug-related discontinuation of treatment, 3) new grade 3 or higher AE (not already present at baseline), and 4) study drug-related new grade 3 or higher AE. The cumulative probability (i.e., risk) of each safety and each tolerability endpoint (4 endpoints) will be estimated using the Kaplan-Meier approach and stratified log-rank test will be employed for between trial arm comparisons (as outlined for the primary efficacy outcome). Follow-up will be right censored at the date of last known status and event times will be the date of first onset of the given endpoint (e.g., time to first AE leading to early discontinuation of blinded treatment).

The safety and tolerability profile of EIDD-2801 in humans is currently not fully characterized and descriptive participant-level listings of safety and tolerability events will be summarized. We will estimate 28-day risk function of each safety and tolerability endpoint with a corresponding 2-sided 90% confidence interval, with focus on the upper confidence limit for interpretation of results. To inform the design of future larger trials we will estimate the difference in probabilities

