(i.e., a risk difference) between randomization arms of each safety and tolerability endpoint with a corresponding 90% confidence interval. A risk ratio may also be estimated for comparison to other studies, although a risk difference is of greater public health relevance.

Endpoints (1) and (2) above may be composited to assess tolerability as any AE leading to early discontinuation of blinded study treatment or any discontinuation of study treatment (active or placebo) deemed related to study drug.

Additionally, we will describe and estimate mortality from any cause or hospitalization during the 28-day period from and including the day of the first (confirmed) dose of study treatment. Hospitalization is defined as requiring at least 24 hours of acute care in a hospital or similar acute care facility, including Emergency Rooms or temporary facilities instituted to address needs during the COVID-19 pandemic. Evaluation at a hospital or similar facility with less than 24 hours of acute care is not considered a hospitalization. The Kaplan-Meier approach described above will be applied to the endpoint of days until death or first hospitalization and the 28-day risk function will be estimated as described for the primary safety endpoints.

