2.3. Statistical Hypotheses

- EIDD-2801 treatment will decrease the time to clearance of SARS-CoV-2 virus in NP specimens from symptomatic SARS-CoV-2 infected adults compared to placebo For study Part 1, the distribution of days until SARS-CoV-2 viral RNA is not detectable (i.e., below the limit of quantification in NP swabs) can be compared between the 2 trial arms (drug vs. placebo) using an exact log-rank test. No hypothesis will be formally tested for study Parts 2-9.
- EIDD-2801 will be safe and well tolerated in persons with symptomatic SARS-CoV-2 infection

The safety and tolerability endpoints will be presented descriptively. No hypotheses for safety and tolerability will be tested.

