5.2. Data Presentation Conventions

Unless otherwise stated, continuous data will be summarized with the following descriptive statistics: number of non-missing observations (n), arithmetic mean, standard deviation (SD), median, minimum (min), maximum (max), and for PK parameters only, geometric mean, SD and geometric CV% for continuous variables. Categorical variables are summarized using counts and percentages. All reported p-values will be 2-sided.

The following conventions are applied to all data presentations and summaries.

- For continuous variables, all mean and median values are formatted to one more decimal place than the measured value. Standard deviation values are formatted to two more decimal places than the measured value. Minimum and maximum values are presented with the same number of decimal places as the measured value.
- For categorical variables, the number and percentage of responses are presented in the form XX (XX.X%) where the percentage is in the parentheses.

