11. CHANGE FROM ANALYSIS PLANNED IN PROTOCOL

Due to lack of availability of subjects in the "early" time from symptom onset stratum, the between group comparison for the time to non-detectable SARS-CoV-2 viral RNA will be performed using an un-stratified log-rank test.

Statistical comparisons of safety endpoints between treatment groups in Part 1 will not be performed. All safety data will be presented descriptively.

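### The SAP does not carry over the per-arm 90% interval that the protocol uses to interpret the Part 1 primary safety endpoints, and does not list this among its changes

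*SAP*

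**What the plan says.** Safety and tolerability is a primary objective in both documents (Protocol 1.2.2, SAP 2.1.1). It has four endpoints: adverse events leading to early discontinuation of treatment, drug-related discontinuation, new Grade 3 or higher events, and drug-related new Grade 3 or higher events.

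Protocol 10.7.3.1 plans three things for each endpoint in Part 1:

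- Risk estimation and a test. The cumulative risk "will be estimated using the Kaplan-Meier approach and stratified log-rank test will be employed for between trial arm comparisons".
- A 28-day risk with a "2-sided 90% confidence interval, with focus on the upper confidence limit for interpretation of results".
- A risk difference "between randomization arms of each safety and tolerability endpoint with a corresponding 90% confidence interval".

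Protocol 10.7.3 also asks that exact "statistical procedures that do not rely on large sample assumptions will be applied where computationally feasible".

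The SAP takes a different line. Section 2.3 says "No hypotheses for safety and tolerability will be tested", and section 11 says "Statistical comparisons of safety endpoints between treatment groups in Part 1 will not be performed. All safety data will be presented descriptively". Under section 5.2, "Categorical variables are summarized using counts and percentages". Section 8.2 lists the adverse event tables. All four endpoints appear there as tabulated treatment-emergent events, but no interval, Kaplan-Meier risk or 28-day risk is listed.

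SAP section 1 gives the SAP precedence over the protocol's statistics and undertakes to identify substantial differences. Protocol 10.7 and 10.8 also let the SAP prevail.

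**The concern.** The protocol did not treat the per-arm interval as decoration: its upper limit was the stated basis for interpreting a primary objective, for a drug whose safety the same section describes as not yet fully characterised. If the SAP is followed as written, that basis disappears and a percentage alone takes its place.

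Dropping tests does not require dropping intervals. The SAP tests no hypothesis in Parts 2 to 9 (section 2.3), yet section 9.1 keeps 95% intervals for the virology results in those parts.

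The risk lies in how a small count is read. A line showing 0 (0.0%) in an arm of 22 or fewer invites the conclusion that the event is rare, which such a sample cannot support.

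**Working it through.** **1. Inputs.** Part 1 plans about 22 participants per arm (Protocol 10.5). The protocol synopsis, under Regimen, lets Part 1 be considered full at 24, which is about 12 per arm if the 1:1 allocation splits evenly. The interval is two-sided 90%, so each tail is 5% (Protocol 10.7.3.1).

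**2. The plan's own figure.** The documents state no precision figure for safety. The arm size reproduces from Protocol 10.5: 19 evaluable per arm with 10% missing gives 19 / 0.90 = 21.1, rounded up to 22.

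**3. Exact upper limit with zero events.** The limit p solves (1 − p)^n = 0.05, so p = 1 − 0.05^(1/n).

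| n in arm | Source of n | Reported under the SAP | Exact two-sided 90% upper limit |
|---|---|---|---|
| 22 | planned size | 0 (0.0%) | 1 − 0.05^(1/22) = 12.7% |
| 20 | about 10% of 22 missing | 0 (0.0%) | 1 − 0.05^(1/20) = 13.9% |
| 19 | evaluable size | 0 (0.0%) | 1 − 0.05^(1/19) = 14.6% |
| 12 | closure at 24 | 0 (0.0%) | 1 − 0.05^(1/12) = 22.1% |

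The point is not confined to zero counts. With 1 event in 22 (4.5%), the exact upper limit is 19.8%.

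**4. How likely a zero count is.** The documents give no expected event rate, so the true risk below is an assumption. P(0 events) = (1 − p)^n.

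- p = 5%: 0.95^22 = 32% and 0.95^12 = 54%.
- p = 10%: 0.90^22 = 10% and 0.90^12 = 28%.

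At the minimum arm size, a true risk of 10% would therefore produce an empty row more than one time in four.

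**5. Whether restoring the protocol text is enough.** It may not be. With no events the Kaplan-Meier estimate of event-free probability stays at 1 and its Greenwood variance is 0, so the usual interval collapses to 0 to 0. An exact method has to be named, which also fits the preference in Protocol 10.7.3.

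**6. The time window.** The protocol's quantity is a 28-day risk. SAP 8.2 counts an event as treatment-emergent only up to 14 days after the last dose and tabulates later events separately. Dosing ends on Day 5, or Day 6 where extended, so that window closes about Day 5 + 14 = 19 or Day 6 + 14 = 20, and earlier for a participant who stops early. An interval attached to the existing tables would not bound the 28-day risk.

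**7. What section 11 declares.** It names the removal of between-group comparisons, which covers both the log-rank test and the risk difference. It does not name the per-arm risk or its interval.

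**The case against.** The strongest reply is that the SAP never says the per-arm interval is removed. The loss is inferred from the word descriptive, the counts-and-percentages convention (which applies unless otherwise stated) and the absence of any interval in section 8.2. Elsewhere the documents use descriptive loosely, even for p-values, and the display specifications sit in a separate document that cannot be checked here. This stands as a caution: the SAP fails to specify the interval rather than expressly cancelling it. But an estimate on which a primary objective is to be interpreted belongs in the SAP itself, and a SAP that overrides the protocol does not keep the protocol's text by silence.

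A second reply is that little is lost in practice. Counts and denominators will be reported, so any reader can compute the limit, and no stated decision rule uses it. That is true: the loss is in pre-specified reporting, not in the data.

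A reader might also infer two stronger criticisms that the documents do not support:

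- **That the SAP dropped the risk difference without saying so.** A risk difference between arms is a between-group comparison, and section 11 openly declares that these will not be performed. One may disagree with that choice, but it is disclosed, and the protocol lets the SAP prevail.
- **That planned intervals for the pooled dose groups were lost.** The protocol's 90% interval belongs to Part 1, and Protocol 10.8 says that safety data will be provided descriptively by dose group. Limits for pooled groups therefore do not measure what was lost.

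**Conclusion.** The point holds for the per-arm interval in Part 1 and no further. The protocol interprets four primary safety endpoints through an upper 90% limit; the superseding SAP does not provide for it and neither names nor explains the change. With no events, the unreported limit is 12.7% at 22 per arm and 22.1% at 12 per arm.

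These figures assume a zero count, an even split if Part 1 closes at 24, and complete follow-up to Day 28. Zero events is a scenario, not a forecast: COVID-19 progression, including hospitalization, is collected as adverse events (Protocol 7.3.4), so some Grade 3 or higher events may well occur. The interval is still needed if they do.

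This is more than missing detail, because following the SAP as written removes the protocol's stated basis for interpretation. It should be corrected, but it does not threaten the validity of the trial.

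**What to change.** In SAP 8.2, for Arms A and B, add a table of the four primary safety and tolerability endpoints. For each endpoint and arm, give the number of participants with at least one event from Day 1 to Day 28, the denominator, the percentage, and the exact (Clopper-Pearson) two-sided 90% interval. State that the window is Days 1 to 28 and is not limited to the treatment-emergent window ending 14 days after the last dose. Keep the decision in section 11 not to compare arms. If the sponsor does intend to drop the per-arm interval, section 11 should say so and give the reason.

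The same interval for pooled dose groups, or a risk difference with its interval, would be optional additions.

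The cost is one further small table and a second event window to program. The statistical price is that a crude proportion ignores censoring, unlike the protocol's Kaplan-Meier risk. This matters little if few participants are lost before Day 28; Protocol 10.7.3 expects missing data in no more than about 5 to 10%. Excluding 2 of 22 participants would move the zero-event limit from 12.7% to 13.9%.

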12. ATTACHMENTS

12.1. Table of Contents for Data Display Specifications

The TOC will be provided in a separate document.
